4.3. Primary endpoint

The primary endpoint of this study is reduction of gingivitis (change from baseline) as measured by BOP and MGI at baseline, and again at 12-week visits.

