The first follow-up will take place two weeks after the baseline visit. Subjects can schedule the visit for any time between two days before and after the two-week use period (12-16 day range). Clinical examinations will be given to the subjects in the same order as the baseline visit with the exception that no second plaque index will be recorded. All subjects must present with 7 to 12 hours of undisturbed plaque. The oral safety exam will include a thorough examination of the gingiva to look for any signs of gingival trauma, irritation or abrasion. Any subjects who show signs of gingival trauma that appears to be toothbrush related will be exited from the study. The recorded findings will be reported as Adverse Events. In addition, any site in the mouth that shows an increase in probing pocket depth of 2 mm or greater from the baseline measurement will have that particular site treated with subgingival scaling and root planing or whatever the PI deems appropriate therapy. If subjects meet any of the discontinuation criteria, they will be withdrawn from the study.

Visit 4: Four-week follow-up

This visit should take place four weeks after the baseline visit within three days before and after the four week mark (25-31 day range). Subjects will receive full mouth examinations in the same order as the previous visit. Additionally, inspection for signs of gingival trauma and increase in PPD greater than 2 mm from the baseline will be conducted and evaluated. The PI will determine if any subject meets the discontinuation criteria as well as appropriate therapy to treat.

Visit 5: 12-week follow-up

In this visit, subjects will return the products, including manual toothbrush, or brush head, brush handle, and charger. The procedure is similar to the four-week follow-up visit, in which full mouth clinical examination will be carried out as before on each of the subjects. The subjects' disclosed plaque will be evaluated as usual. The examined results will be recorded. Prophylaxis will be carried out as needed.

The used brushes/brush heads will be returned to sponsor at the end of the trial and examined for wear as an additional measure of compliance.

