5.2. Exclusion Criteria

Any subject meeting one of the following criteria will not be included in the study.

1. Daily user of interdental cleaning devices, such as floss, floss picks, toothpicks, interdental brush, water flossing device
2. Regular user of antimicrobial mouthrinses within one week of entry into study
3. Professional prophylaxis within one month of entry into the study
4. Use of antibiotics within one month prior to the baseline exam
5. Signs of moderate to severe periodontitis or caries, categorized as PPD of 5 mm or higher and attachment loss of 3 mm or higher
6. Subjects with orthodontic bands and/or dental appliances.
7. Participated in an oral care related study in the last 90 days prior to this study
8. Pregnant or lactating women
9. Patients with a history of significant cardiovascular disease, diabetes, cancer, AIDS, or other organ impairment that would preclude their participation in the study
10. Acute/concurrent illness such as hepatitis, herpes simplex infections, influenza, etc.
11. History of rheumatic fever, cardiovascular valvular disease, artificial joint replacement or kidney or liver disorders
12. Chronic use of NSAID's (≥ 325 mg/day)
13. Current Smoker (within the last 3 months)
14. Other medical or dental conditions that would affect the study
15. Inability to commit to all necessary study visits from baseline to 12 weeks

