5.3. Discontinuation criteria

The oral safety exam at the follow-up visits will include a thorough examination of the gingiva to look for any signs of gingival trauma, irritation or abrasion, as well as a periodontal probing. Any subjects who show signs of gingival trauma that appears to be toothbrush related will be exited from the study and the findings reported as Adverse Events. In addition, subjects may be discontinued due to the following reasons.

1. Voluntary discontinuation: subjects are free to discontinue their participation in the study at any time.
2. Safety concerns: the principal investigator may terminate a subject's participation if gingival trauma occurs and appears to be toothbrush related
3. Significant non-compliance to protocol: the principal investigator may terminate a subject's participation if subjects are shown to be non-compliant to the protocol
4. Incorrect enrollment: subjects who did not meet admission/exclusion criteria
5. Subject received any type of dental treatment/care other than those required in the study, for example use of interdental devices, mouthrinses, chewing gum or prophylaxis treatment, without consent of the investigator

Subjects who discontinue should be asked to a follow-up visit to observe any Adverse Events.

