7. STATISTICAL ANALYSIS

Each of the two research groups' patients will be assessed clinically at four time points (Baseline, 2 weeks, 4 weeks and 12 weeks). These measures will be compared against one another and over time using a between-within factors repeated measures ANOVA.

Further evaluation of interproximal and marginal scores will also be evaluated with a post hoc analysis.

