7.1. Sample size

Assuming an alpha/p-value of 0.05, and a power of 0.95, the minimum number of subjects needed (after all drop-outs have been removed) is 44. Due to the length of the study and multiple visits required within the length of the study, the potential for moderately high drop-out rates is set at 40%. 72 subjects will be initially enrolled; 36 will be assigned to the power toothbrush group, and 36 will be assigned to the manual toothbrush group.

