7.4. Method

Reductions in gingivitis – BOP, MGI and PPD – and plaque – PI from baseline scores after 2 weeks, 4 weeks and 12 weeks of use will be evaluated. For each subject, mean score of each index will be calculated as well as reductions from baseline at three time points. Additionally, numbers of abrasion sites found will be compared.

Assuming evaluated scores for the test and control groups are denoted U_{Test} and U_{Control} , respectively, the null hypothesis will be tested.

$$H_0: U_{\text{Test}} - U_{\text{Control}} = 0$$

$$H_1: U_{\text{Test}} - U_{\text{Control}} \neq 0$$

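### With 40% drop-out planned, the only named analysis is a four-visit repeated-measures ANOVA, with no all-randomised analysis and no missing-visit rule

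*Combined protocol and SAP*

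**What the plan says.** - **Method.** Section 7 lists four assessment times (baseline, 2, 4 and 12 weeks) and one model: "These measures will be compared against one another and over time using a between-within factors repeated measures ANOVA". No mixed-model form is specified.
- **Primary endpoint.** Section 4.3 defines it as "reduction of gingivitis (change from baseline) as measured by BOP and MGI at baseline, and again at 12-week visits". MGI and BOP reductions at weeks 2 and 4 are secondary (Section 4.4).
- **Derived scores.** Section 7.4: "For each subject, mean score of each index will be calculated as well as reductions from baseline at three time points". It adds a two-sided hypothesis but no model, analysis set or missing-data rule.
- **Sizing.** Section 7.1: "the minimum number of subjects needed (after all drop-outs have been removed) is 44", and "the potential for moderately high drop-out rates is set at 40" percent. Enrolment is 72, 36 per arm.
- **Exit.** Under Visit 3 in Section 4.5: "If subjects meet any of the discontinuation criteria, they will be withdrawn from the study". That visit's text and the opening of Section 5.3 also require exit for gingival trauma that looks brush-related; item 2 of Section 5.3 words the same exit as discretionary. Afterwards: "Subjects who discontinue should be asked to a follow-up visit to observe any Adverse Events". Whether MGI or BOP is scored at that visit is not said.
- **Exclusion of data.** The only rules act within the mouth: surfaces graded 9 (Sections 4.2.2 and 4.2.3) and teeth with calculus (Section 7.2).

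**The concern.** A classical between-within ANOVA needs a complete row of visits for each subject. Combined with 40% planned loss and no stated analysis set, the default is a comparison of completers, and the choice of who counts could be made after the data are seen.

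Two things are at stake. First, week-2 and week-4 scores already taken on leavers would not help to estimate the week-12 difference. Second, if leaving is related to gingival response, completers are a selected group. The comparison can be shifted if the selection differs by arm, or diluted if the same selection acts in both arms and the brush works. The plan contains one exit route that could differ by arm, brush-related trauma, because the brush is what differs.

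**Working it through.** **1. The plan's own figures.** Inputs from Section 7.1: 44 completers, 40% drop-out, 72 enrolled.
- 44 / (1 − 0.40) = 73.3, rounded up to 74, against 72 stated. This is close enough, so the enrolment figure is not at issue.
- 72 allows for drop-out of 1 − 44/72 = 38.9%.
- The 44 itself cannot be reproduced, because no effect size, SD or within-subject correlation is given.

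**2. Who is left out.**
- Leavers: 72 × 0.40 = 28.8, about 29.
- Subjects with all four visits: 72 × 0.60 = 43.2, about 43, if those who stay miss no visit.
- Leavers' follow-up visits that do not inform week 12: from 0 (all leave before week 2) to 2 × 28.8 = 57.6, about 58 (all leave after week 4).

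**3. Two readings of the analysis.** Under Section 7 read as a classical ANOVA, any missed visit removes the subject. Under Section 7.4, reductions are computed visit by visit, so a missed week-2 or week-4 visit need not remove anyone and a leaver's early scores can enter the secondary comparisons. Under both readings, a leaver has no planned week-12 score and drops out of the primary comparison.

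**4. Illustrative simulation.** None of these inputs is in the documents except 36 per arm, four visits and roughly 40% loss. Assumed: equal visit correlation of 0.3, 0.5 or 0.7; 10% lost at random before week 2, then 18% at each of two steps (0.90 × 0.82 × 0.82 = 0.605 retained); exit logistic in the last observed change, slope 0.5 or 1.0 per SD. The model is maximum likelihood with unstructured covariance and a common baseline mean. Units are SD of change.

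| Scenario | Unadjusted completers | Baseline-adjusted completers | Likelihood model |
|---|---|---|---|
| SE, random exit, correlation 0.5 | 0.305 | 0.267 | 0.263 |
| Bias, one arm, slope 0.5, no true difference | 0.083–0.088 | 0.029–0.058 | ≤ 0.003 |
| Bias, one arm, slope 1.0, no true difference | 0.151–0.156 | 0.049–0.107 | ≤ 0.002 |
| Same rule in both arms, no true difference | ≤ 0.004 | ≤ 0.004 | ≤ 0.004 |
| Dilution, same rule in both arms, true benefit 1.0 SD | 0.03–0.10 | 0.01–0.07 | < 0.005 |

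Repeat runs of similar set-ups widen the one-arm ranges to about 0.08–0.18 (unadjusted) and 0.02–0.13 (adjusted).

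Hand check of the SEs: completers per arm are 36 × 0.605 = 21.8, so the unadjusted SE is √(2/21.8) = 0.303. Baseline adjustment multiplies it by √((1 + 0.5)/2) = 0.866, giving 0.262. Both agree with the simulation to within small-sample loss.

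**5. Error rates with no true difference.** With one-arm response-related exit, unadjusted completers reject in 5.8% to 8.2% of trials and adjusted completers in 5.2% to 6.6%. The group-by-time F-test on completers, which is nearest to the named method, rejects in 6% to 7% at slope 0.5 and about 11% at slope 1.0. The likelihood model with an uncorrected normal test rejects in 6.0% to 6.8%, even under random exit, so it needs a small-sample correction.

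**The case against.** The strongest case against is that the harm is hypothetical. Section 7.1 attributes the 40% to study length and number of visits, which are common to both arms. Section 5.2 excludes people with "Inability to commit to all necessary study visits from baseline to 12 weeks", weeks 2 and 4 have date windows, and visits are reimbursed (Section 11). No passage suggests that exit depends on MGI or BOP response. The exit timings, slopes and correlations are assumed, and the simulated exit depends on observed scores, which is the case the likelihood model is built for. Even then, the adjusted-completer bias at slope 0.5 is at most 0.058/0.285 = 0.20 of a standard error (correlation 0.7), and nearly all the precision gain comes from baseline adjustment.

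All of that stands, and it limits the size of the point. It does not fill the gap: the sponsor still plans for 40% loss, and no analysis set or missing-visit rule is given.

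Three stronger readings are tempting and are not supported:
- A reader might infer that leavers' interim scores are wasted. Sections 4.4 and 7.4 allow them into the week-2 and week-4 comparisons.
- A reader might infer that nothing is scored after exit. Section 5.3 asks for an adverse-event visit and is silent on scoring.
- A reader might infer that the plan prescribes a completer-only analysis. The method and the Section 7.1 phrase imply it, but that phrase concerns sample size and does not define an analysis set.

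**Conclusion.** The point holds as a gap in the primary analysis that is cheap to close. At the planned drop-out, the named method in its classical form rests on about 43 of 72 randomised subjects, and no rule covers the other 29. That conclusion needs only the documents and the standard complete-data requirement of the classical ANOVA.

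Whether bias would follow is not shown. It would require exit related to response and either differing by arm or acting on a real benefit. Trauma exit makes an arm difference possible, but it was not itself simulated, and the figures above illustrate scale only. Confidence is medium.

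**What to change.** For the primary analysis, replace the ANOVA with a likelihood-based repeated-measures model of all randomised subjects in their assigned arm. Specify baseline adjustment, unstructured covariance, a small-sample degrees-of-freedom correction such as Kenward-Roger, and a week-12 contrast for MGI and for BOP. Use all week-2 and week-4 data from leavers.

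Also state in the plan:
- Scoring after exit is not specified, so the model estimates the week-12 difference had subjects remained in the study. That wording also suits subjects who stay but receive site scaling or prophylaxis (Sections 4.5 and 5.4).
- Drop-out and reasons, including trauma exits, will be reported by arm.
- Sensitivity analyses will be a baseline-adjusted completer analysis and a missing-not-at-random scenario, for example leavers assumed unchanged from baseline.

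The cost is plan wording and slightly more analysis, with no added visits, measurements or subjects. The model relies on a missing-at-random assumption and would be biased if exit depended on unobserved scores, which the last scenario probes. Subjects with no follow-up visit add almost nothing. The precision gain over baseline-adjusted completers is small (SE 0.263 against 0.267 at correlation 0.5); the main gain is protection if exit is response-related.

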7.1. Sample size

Assuming an alpha/p-value of 0.05, and a power of 0.95, the minimum number of subjects needed (after all drop-outs have been removed) is 44. Due to the length of the study and multiple visits required within the length of the study, the potential for moderately high drop-out rates is set at 40%. 72 subjects will be initially enrolled; 36 will be assigned to the power toothbrush group, and 36 will be assigned to the manual toothbrush group.

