4.5. Study procedure

The study to be conducted will be single-blinded, randomized controlled, parallel design. The study population will consist of Seventy-two (72) male and female subjects conforming to the following admission criteria. The subjects meeting the admission criteria with an anticipation of 40% dropout rate will be stratified into two groups balanced for MGI, BOP, PI, and gender using screening data. In this single-blind design, product assignment will be randomized after screening, and only the PI and the Study coordinator will have access to the randomization key.

One group will be assigned to a new power toothbrush while the control group will be assigned an ADA approved manual toothbrush. The study involves a 12-week home use of the respective toothbrushes. Both groups will refrain from the regular use of mouthwash and any interdental device, such as floss, floss picks, toothpicks, water flossing device or interdental brush, during the length of the study. Written instructions on brushing and professional brushing demonstration will be provided at the outset of the study and each participant from both test and control groups will also receive a 2-minute timer to help them monitor their brushing time. Before each visit, subjects are expected to have at least 7 hours, but no more than 12 hours of accumulated, non-brushed, undisturbed plaque/debris.

The study includes four or five visits – screening, baseline, 2-week follow-up, 4-week follow-up and 12-week follow-up. Schematic 1 summarizes the study procedure and visits and Table 2 details procedures in this study. The Screening and the baseline visit may happen on the same day.

Schematic 1. Study and visit procedures

CONFIDENTIAL

CONFIDENTIAL

Visit 2: Baseline
(continued)

A

Use brush per instruction

PI examination after
brushing

Single use
result

Schedule next visit

Pre visit

7 – 12 hours of plaque
accumulation

Visit 3: Follow-up visit
at 2 weeks

Oral examination for tissue abrasion and MGI
by calibrated examiners

Periodontal probing for BOP and PPD
by calibrated examiners

Oral examination for PI
By calibrated examiners

Schedule next visit

Pre visit

7 – 12 hours of plaque
accumulation

Visit 4: Follow-up visit
at 4 weeks

[figure not shown]
Oral examination for tissue abrasion and MGI
by calibrated examiners

Periodontal probing for BOP and PPD
by calibrated examiners

Oral examination for PI
by calibrated examiner

Schedule next visit

A

CONFIDENTIAL

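### Does enrolling 72 with 40% drop-out fall short of the plan's own minimum of 44 completers?

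*Combined protocol and SAP*

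**What the plan says.** Section 7.1 (Sample size) sets out the whole calculation in one paragraph. The error rates come first: "Assuming an alpha/p-value of 0.05, and a power of 0.95". It then states that "the minimum number of subjects needed (after all drop-outs have been removed) is 44". For losses, "the potential for moderately high drop-out rates is set at 40" per cent. Enrolment follows: "72 subjects will be initially enrolled; 36 will be assigned to the power toothbrush group", "and 36 will be assigned to the manual toothbrush group".

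Section 4.5 (Study procedure) repeats the same two planning figures: "The study population will consist of Seventy-two (72) male and female subjects", and eligible subjects are to be stratified into two groups "with an anticipation of 40% dropout rate".

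Neither section says how fractions of a subject are rounded. Neither gives an effect size, standard deviation or within-subject correlation behind the 44. Section 7.4 (Method) states a two-sided alternative.

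**The concern.** The plan calls 44 a minimum, and the drop-out allowance beside it is meant to show that enrolment delivers that minimum. The obvious check multiplies the total by the completion rate and gives 43.2, which is below 44. Inflating 44 by the usual formula gives 73.3, or 74 when rounded up, and not 72. On a strict count the figures agree only with 28 or fewer drop-outs (38.9%), because a 29th leaves 43. The two sections that give these numbers do not address the gap.

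If enrolment really fell short of its own requirement, the trial would be planned to finish with less than its stated 95% power under the losses it expects. A shortfall of several subjects per arm would deserve correction before enrolment closes. The question is whether the difference here is of that kind.

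**Working it through.** **Inputs**

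| Quantity | Value | Source |
|---|---|---|
| Minimum completers | 44 (22 per arm at equal allocation) | 7.1 |
| Drop-out | 40% | 7.1 and 4.5 |
| Enrolled | 72, as 36 + 36 | 7.1; total also in 4.5 |
| Significance level, power | 0.05, 0.95 | 7.1 |
| Sidedness | two-sided | 7.4 |

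**1. Reproducing the plan's figure.** Completers per arm = enrolled per arm × (1 − drop-out) = 36 × 0.60 = 21.6, which is 22 to the nearest whole subject. Two arms give 2 × 22 = 44. Counting losses gives the same answer: 36 × 0.40 = 14.4, nearest whole number 14, and 36 − 14 = 22. The stated 72, 40% and 44 agree on this reading.

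**2. The inflation in the other direction.** Enrolled = completers / (1 − drop-out) = 44 / 0.60 = 73.3, or 74 rounded up. Per arm, 22 / 0.60 = 36.7, or 37 rounded up. The stated 72 is 1.3 below the unrounded 73.3 and 2 below 74. The common mistake of multiplying by (1 + drop-out) would give 44 × 1.40 = 61.6, or 62. The plan's 72 is nowhere near that, so it did not use the wrong formula.

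**3. Size of the gap without rounding.** 72 × 0.60 = 43.2, and 44 − 43.2 = 0.8 of a subject. The drop-out that leaves exactly 44 is 28 / 72 = 38.9%, and 40 − 38.9 = 1.1 percentage points. One more loss is 29 / 72 = 40.3% and leaves 43.

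**4. Comparison with chance variation.** If each subject independently drops out with probability 0.40, the number of completers among 72 has standard deviation √(72 × 0.60 × 0.40) = √17.28 = 4.16. The gap of 0.8 is 0.8 / 4.16 = 0.19 of one standard deviation.

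**5. Effect on power.** The plan gives no effect size, so this is an illustration only. Assume an unadjusted two-sample comparison, two-sided at 0.05, and the difference for which 22 per arm gives 95% power. By normal approximation that difference is (1.960 + 1.645) × √(2/22) = 1.087 standard deviations.

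| Completers | Power, normal approximation |
|---|---|
| 44 | 95.0% |
| 43.2 | 94.7% |
| 43 | 94.6% |
| 42 | 94.1% |

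A noncentral t calculation, with the difference reset to give 95.0% at 22 + 22, gives 94.5% at 22 + 21.

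**The case for a change.** The best case for the concern is that a minimum should be met and not reached by rounding 43.2 upward. Standard practice rounds enrolment up, which would give 74. The rounding convention also matters: rounding the total number of losses (28.8 to 29) leaves 43, and taking 15 losses per arm leaves 21 + 21 = 42. Since 40% is what the plan expects and not a remote worst case, the boundary between 28 and 29 losses lies where the plan expects to finish.

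Part of this stands. The arithmetic is right, the plan states no rounding rule, and a more cautious author would have written 74.

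It does not amount to an error, for three reasons. First, the plan gives its allocation by arm, and nearest rounding within an arm yields its own figure. The 42 requires 14.4 to be rounded up to 15, which is not nearest rounding. Second, the 40% is worded in both sections as something potential or anticipated. A forecast in round figures is not accurate to 1.1 percentage points, and 38.9% is 40% to the nearest five. Third, the available remedies improve little. Restating drop-out as 38.9% only works the forecast backwards from the enrolment number, with no evidence that it is the better expectation, and it could be misread as a cap on losses. Enrolling two more subjects would settle the rounding but would change the expected completers only from 43.2 to 74 × 0.60 = 44.4.

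**Conclusion.** The concern does not hold. The figures in 7.1 and 4.5 reproduce within ordinary rounding: 36 per arm with 40% loss is 22 per arm, or 44 in total. The unrounded gap is 0.8 of a subject, or 1.1 percentage points of drop-out, well inside both the precision of a round forecast and the chance variation in the number who complete. The illustrated loss of power is about half a percentage point for one subject fewer. That illustration assumes a two-sample t-test, whereas section 7 plans a repeated measures analysis of variance, and it uses an effect size worked back from 44. The conclusion rests on reading the drop-out allowance per arm with nearest rounding, which the plan's 36 + 36 split supports but does not state. On the stricter reading the difference is still too small to alter enrolment, analysis or interpretation. The basis of the 44 itself is a separate matter, which this check neither confirms nor questions.
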